2.3 Rationale

Heparin-induced thrombocytopenia type-II (HIT) is a common and often severe complication of heparin therapy. Although the central feature of HIT is thrombocytopenia, the more worrisome complication is the development of arterial or venous thrombosis often referred to as heparin-induced thrombocytopenia-thrombosis syndrome (HITT). The exact incidence of HIT associated thrombosis is not well established but studies demonstrate a range from 10% to as high as 55%.⁴ In addition, the mortality associated with this complication has been reported to be as high as 20%.^{4,9,10} Given this high rate of mortality and the awareness of prolonged thrombin generation even after heparin is discontinued, establishing the diagnosis, discontinuing heparin therapy and immediately intervening with a non-heparin anticoagulant are critical for preventing thromboembolic complications (TEC).⁸

Presently there is only one available alternative (Argatroban) to heparin that is FDA approved for HIT or HITT in this country that can be used as a bridge to coumadin.^{9,10} Argatroban is a direct thrombin inhibitor (DTI), administered intravenously, requires continuous laboratory monitoring, can cause excessive bleeding and is extremely costly. Non FDA agents that are often used are fondaparinux or bivalirudin, the former requires an injection and the later is similar to Argatroban (and is approved for HIT in patients undergoing PCI). Practice standards require therapeutic anticoagulation with a DTI until platelet count recovery, followed by 5 or more days of overlap while transitioning to oral warfarin with goal INR 2-3 for 1 month for patients with HIT and 3 months for patients with HITT.^{8,11} Thus, anticoagulating patients with HIT has

become a huge expense and burden on our health care system.

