- The diagnosis of **skin necrosis** will be considered confirmed if accompanied by symptoms or signs consistent with an event, accompanied by skin biopsy, expert consultation by a dermatologist and/or objective review of a high-resolution photograph of the involved integument by an appropriate specialist.
- The circumstances of any **sudden death** will be reviewed by the DF/HCC Data and Safety Monitoring Committee (DSMC) per Section 12.2.

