13 STATISTICAL CONSIDERATIONS

13.1 Study Design/Endpoints

This is a prospective, open label, single center study designed to evaluate the activity and tolerability of apixaban for the treatment of hospitalized patients with a confirmed diagnosis of isolated heparin induced thrombocytopenia (HIT).

Standard therapy with argatroban in isolated HIT has been associated with an estimated 6-8% incidence of new TEC (approximately 7%). However, the literature also reports mortality rates of up to 20% within 30 days of initiation of argatroban therapy. Furthermore, two recent “real world” analyses revealed a much higher risk of death, limb amputation and new thrombosis than was reported in prior studies.^{13,14}

The primary endpoint of this study is to evaluate the activity of the oral factor Xa inhibitor, apixaban as monotherapy in patients with heparin induced thrombocytopenia (HIT) and heparin

inducted thrombocytopenia with thrombosis (HITT), as defined by the incidence of new symptomatic thromboembolic complications (TEC) within 30 days of the time of initiation of apixaban.

The proportion of patients with confirmed HIT who are alive without new TEC at day 30 will be reported as a binomial proportion. We will also report the rate of new TEC, as estimated in the context of a cumulative incidence model in which death before day 30 in the absence of new TEC is treated as a competing risk.

Based on a recent “real world” analysis, where ¼ patients had HITT and ¾ patients had isolated HIT, the proportion of patients alive and without TEC was 59% in the HITT group and 66% in the isolated HIT group.¹⁴ We calculated the expected proportion of patients alive and without TEC for this present study based on the proportion of patients and event rates in each group from the real world analysis.

A total of 49 patients with a diagnosis or high clinical suspicion for HIT will be enrolled in this study using a one-stage design. We assume a conservative 10% frequency of negative confirmatory testing, thus yielding at least 44 patients with confirmed HIT in whom to assess the efficacy of this treatment at the conclusion of the trial. We anticipate that we will accrue and complete follow up on all patients within 2 years, based on investigators’ estimates of incident cases of HIT at MGH.

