If at least 34 of 44 confirmed HIT patients are alive without new TEC at day 30, we will consider the study a success. The lower bound of the exact 90% confidence interval associated with this outcome is 0.65, suggesting that if we observe a 77% success rate, the probability that the true but unknown success rate is less than 65% is less than 0.05. We note again that in this calculation, both new TEC or death without TEC by day 30 are considered failures. We will also estimate the rate of new TEC at day 30 using the cumulative incidence model, and provide a 90% confidence interval based on the model estimate of variance.

A descriptive analysis of the secondary efficacy endpoints will be obtained.

Exact binomial 90% confidence intervals will be provided.

Demographic and baseline characteristics will be summarized overall using descriptive statistics (mean, median, standard deviation, minimum, and maximum) for continuous variables (e.g., age) and counts and percents for categorical variables (e.g., gender or race).

90% EXACT BINOMIAL CONFIDENCE INTERVALS FOR VARIOUS OBSERVED PROPORTIONS OF PATIENTS ALIVE WITHOUT NEW TEC AT DAY 30

Observed Response Rate	90% CI
-------------------------------	---------------

32/44 (73%)	(60% to 83%)
34/44 (77%)	(65% to 87%)
36/44 (82%)	(70% to 91%)

13.2 Sample Size, Accrual Rate and Study Duration:

See Section 13.1 above.

Both men and women of all races and ethnic groups are eligible for this trial. It is hoped that the accrual targets will resemble the gender, ethnic, and racial composition of the U.S. population as closely as possible.

13.3 Interim Monitoring Plan:

The study will be suspended for toxicity review if 5 or more patients out of the first 15 experience major hemorrhagic or thrombotic complications. The following table summarizes the probability of suspension given various probabilities of major hemorrhagic or thrombotic complications.

Probability of major hemorrhagic or thrombotic complications	0.13	0.20	0.33	0.40
Probability of suspension	0.04	0.16	0.60	0.78

Suspension will also be warranted if death without new TEC occurs in 2 or more of the first 15 patients. The following table summarizes the probability of suspension given various probabilities of death without new TEC.

Probability of death without new TEC	0.10	0.13	0.20	0.25
Probability of suspension	0.45	0.61	0.83	0.92

13.4 Analysis of Primary Endpoints:

See section 13.1

13.5 Analysis of Secondary Endpoints:

See section 13.1

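### The early mortality trigger in Section 13.3 counts only deaths without new TEC, so the chance of suspension at a given total mortality depends on how many deaths follow a TEC

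*Combined protocol and SAP*

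**What the plan says.** Section 13.3 (Interim Monitoring Plan) gives two suspension rules for the first 15 patients.

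- Complication rule: "The study will be suspended for toxicity review if 5 or more patients out of the first 15 experience major hemorrhagic or thrombotic complications".
- Death rule: "Suspension will also be warranted if death without new TEC occurs in 2 or more of the first 15 patients".

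Each has its own table of suspension probabilities. The complication table covers event probabilities 0.13, 0.20, 0.33 and 0.40, and the death table covers 0.10, 0.13, 0.20 and 0.25. The death table is explicitly confined to deaths without TEC: "The following table summarizes the probability of suspension given various probabilities of death without new TEC". No joint probability for the two rules is given.

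The category comes from the efficacy analysis. Section 13.1 says that "death before day 30 in the absence of new TEC is treated as a competing risk", and counts both new TEC and death without TEC as failures against the success criterion.

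On background mortality, Section 13.1 notes that "the literature also reports mortality rates of up to 20% within 30 days of initiation of argatroban therapy". It does not divide those deaths by whether a new TEC came first.

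Section 12.2 has the DSMC review toxicity and accrual up to four times a year, or more often if needed. A summary of deaths within 30 days is among the items it may receive. No numerical mortality threshold is attached to that review.

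**The concern.** Splitting failures into TEC and death without TEC is sound for a competing-risk analysis, where the two categories together make up all failures. Used as a safety trigger, the same split gives deaths different thresholds. Two deaths unconnected with thrombosis suspend the study. Two deaths from new pulmonary embolism or stroke do not, because each is only one of the five complications needed.

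A fatal new TEC is the gravest form of the outcome that apixaban is meant to prevent. The trial is open-label with no control arm, so no concurrent comparison would show excess deaths, and the early rules are the only pre-specified safeguard. If mortality among the first 15 patients were high because the drug was failing, these rules would respond less often than if it were equally high for other reasons.

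**Working it through.** **Inputs from Section 13.3.** n = 15; death rule at 2 or more; complication rule at 5 or more; the two printed tables. The 20% mortality figure is from Section 13.1.

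**Assumptions, not in the documents.** The share of deaths that follow a new TEC, and the rate of non-fatal TEC or major bleeding. Deaths without TEC are taken not to be major bleeds; a fatal major bleed would count under both rules.

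**Step 1: reproduce the printed tables.** The formula is the exact binomial tail P(X ≥ k) with n = 15.

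| Rule | Event probability | Printed | Recomputed |
|---|---|---|---|
| Death, k = 2 | 0.10 | 0.45 | 0.451 |
| | 0.13 | 0.61 | 0.599 (0.613 at 2/15) |
| | 0.20 | 0.83 | 0.833 |
| | 0.25 | 0.92 | 0.920 |
| Complication, k = 5 | 0.13 | 0.04 | 0.036 (0.040 at 2/15) |
| | 0.20 | 0.16 | 0.164 |
| | 0.33 | 0.60 | 0.585 (0.596 at 1/3) |
| | 0.40 | 0.78 | 0.783 |

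The printed figures are right, allowing for rounded column labels. The issue is which deaths are counted.

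**Step 2: both rules together at 20% mortality.** Let *a* be deaths after new TEC and *c* deaths without it, with probabilities p_a + p_c = 0.20 and no other major complications. Then

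P(suspend) = 1 − Σ(c = 0 to 1) Σ(a = 0 to 4) [15! / (a! c! (15 − a − c)!)] p_a^a p_c^c 0.80^(15 − a − c).

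With p_a = p_c = 0.10, the c = 0 terms sum to 0.202 and the c = 1 terms to 0.338, so P(suspend) = 1 − 0.540 = 0.46. Other splits, and the same with an added 5% of non-fatal major complications:

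| Share of deaths after TEC | No other complications | Plus 5% non-fatal |
|---|---|---|
| 0% | 0.83 | 0.83 |
| 25% | 0.68 | 0.69 |
| 50% | 0.46 | 0.49 |
| 75% | 0.23 | 0.32 |
| 100% | 0.16 | 0.31 |

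An all-cause death rule at the same threshold gives 0.83 in every row.

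**Step 3: deaths with neither rule met.** At the even split with no other complications, three or more deaths without suspension has probability 0.043 (c = 0, a = 3 or 4) + 0.157 (c = 1, a = 2, 3 or 4) = 0.20. The largest possible number is 4 deaths after TEC plus 1 non-bleeding death without TEC, which is 5 of 15. Its probability at the even split is [15! / (4! 1! 10!)] × 0.10^4 × 0.10 × 0.80^10 = 15,015 × 0.00001 × 0.1074 = 0.016. At 75% after TEC it is 15,015 × 0.15^4 × 0.05 × 0.1074 = 0.041.

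**Step 4: effect of counting all deaths.** Joint probability of suspension, with the complication rule unchanged:

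| Fatal TEC | Non-fatal TEC or major bleed | Other death | As written | All deaths counted |
|---|---|---|---|---|
| 2% | 5% | 5% | 0.17 | 0.28 |
| 2% | 5% | 10% | 0.45 | 0.55 |
| 5% | 5% | 5% | 0.18 | 0.45 |
| 10% | 5% | 2% | 0.10 | 0.55 |
| 15% | 2% | 2% | 0.13 | 0.75 |

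**The case against.** The strongest defence is that fatal TECs are already watched. Each counts toward the complication rule alongside every non-fatal TEC and major bleed. The DSMC can meet more often if required and may see a summary of deaths. Serious adverse events go to the Overall PI, and to the manufacturer within 24 hours. All of this stands, so a reader who inferred that the plan is blind to fatal treatment failure would be going too far. What the defence does not supply is a pre-specified threshold for total deaths: the DSMC route is discretionary, and the complication rule suspends with probability only 0.16 at a 20% event rate.

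Three other strong readings are tempting and not supported.

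- *That an unexplained sudden death is classed as TEC and so leaves the death count.* Section 11.1.1 lists sudden death but says only that its circumstances "will be reviewed by the DF/HCC Data and Safety Monitoring Committee (DSMC) per Section 12.2". The same section requires objective confirmation of a TEC, so an unconfirmed sudden death most naturally counts as death without new TEC.
- *That the cited 20% mortality is precisely the mortality the trigger leaves out.* Section 2.3 says of HIT-associated thrombosis that "the mortality associated with this complication has been reported to be as high as 20" per cent. Patients with HITT enter with a thrombosis already present, and a death from that presenting clot is still a death without *new* TEC. The figure in Section 13.1 is not split at all.
- *That five early deaths would probably pass unnoticed.* Five is the arithmetic maximum, with probability about 0.02 at an even split and 0.04 at three quarters after TEC.

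The largest contrasts in Step 4 also need most TECs to be fatal (at least two thirds in the last two rows). With 7% TEC or major bleeding in total, of which 2% fatal, the difference is about 0.10.

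Finally, an all-cause rule at 2 of 15 would suspend with probability 0.83 if apixaban merely matched a 20% background. That is a real cost, but the death table already accepts 0.83 when those deaths are without TEC.

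**Conclusion.** The point holds as a design weakness, not as an error in the printed figures. The only numerical mortality trigger omits deaths after a new TEC, so sensitivity to a given total mortality falls as more of the deaths follow treatment failure: from 0.83 to 0.46 to 0.16 at 20% mortality, as the share after TEC goes from none to half to all with no other complications. Allowing 5% non-fatal complications raises the last figure to 0.31 and leaves the pattern unchanged.

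The direction follows from the wording of the two rules. The size rests on the assumed split and complication rates, for which the documents offer no figures. Under low fatal-TEC rates the loss is modest (about 0.10); it becomes large only if fatal TEC is common, which is when a trigger matters most. The change is worth making because it is cheap and leads to a review, not to termination.

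**What to change.** In Section 13.3:

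1. Change the event in the death rule to death from any cause, with or without new TEC, in 2 or more of the first 15 patients.
2. Relabel the table row as the probability of death from any cause. Its printed probabilities remain valid, since the threshold and n are unchanged.
3. State that a fatal TEC also continues to count in the 5-of-15 complication rule.
4. Add the joint probability of suspension under both rules for a few stated combinations of fatal TEC, non-fatal complication and other death.

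The edit is one phrase, one label and a short table. The operating cost is more pauses, and the plan should say so: 0.28 instead of 0.17 with 2% fatal TEC, 5% non-fatal TEC or major bleed and 5% other death; 0.55 instead of 0.45 with 10% other death; and 0.83 if total mortality is at the cited 20%. If the sponsor prefers to keep the present wording, Section 13.3 should say that deaths after TEC are deliberately left to the complication rule and to DSMC judgement, and still give the joint figures.

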13.6 Reporting and Exclusions

13.6.1 Evaluation of Toxicity

All participants will be evaluable for toxicity from the time of their first treatment.

13.6.2 Evaluation of the Primary Efficacy Endpoint

The full analysis (FA) dataset will include all patients that receive at least one dose of study drug. The per protocol (PP) dataset is a subset of the FA dataset, excluding patients that are subsequently ruled out for this diagnosis by negative confirmatory laboratory testing. The primary efficacy analysis will be conducted in the PP data set. All safety analyses will be performed on the FA dataset. The incidence of new TEC following the initiation of apixaban therapy for HIT is the primary efficacy endpoint of this study, however the tolerability and side effects will be monitored as well.

APPENDIX A PERFORMANCE STATUS CRITERIA

ECOG Performance Status Scale	
Grade	Descriptions
0	Normal activity. Fully active, able to carry on all pre-disease performance without restriction.
1	Symptoms, but ambulatory. Restricted in physically strenuous activity, but ambulatory and able to carry out work of a light or sedentary nature (e.g. , light housework, office work).
2	In bed <50% of the time. Ambulatory and capable of all self-care, but unable to carry out any work activities. Up and about more than 50% of waking hours.
3	In bed >50% of the time. Capable of only limited self-care, confined to bed or chair more than 50% of waking hours.
4	100% bedridden. Completely disabled. Cannot carry on any self-care. Totally confined to bed or chair.
5	Dead.

APPENDIX C APIXABAN PACKAGE INSERT

https://www.accessdata.fda.gov/drugsatfda_docs/label/2012/202155s000lbl.pdf

APPENDIX D

Transition to apixaban from other anticoagulants: taken from package insert

2.4 Converting from or to ELIQUIS

Switching from warfarin to ELIQUIS: Warfarin should be discontinued and ELIQUIS started when the international normalized ratio (INR) is below 2.0.

Switching from anticoagulants other than warfarin (oral or parenteral) to ELIQUIS: Discontinue the anticoagulant other than warfarin and begin taking ELIQUIS at the usual time of the next dose of the anticoagulant other than warfarin.

APPENDIX E

Child-Pugh B and C) Definition

Five clinical features are used to assess the severity of liver disease: 1) grade of hepatic encephalopathy, 2) degree of ascites 3) total bilirubin level, 4) serum albumin, and 5) prothrombin time prolongation (measured as INR). The total point score is then used to determine each patient's Child-Pugh class.

Factor	1 point	2 points	3 points
Encephalopathy	None	Altered mood/confusion or inappropriate behavior, impending stupor, somnolence	Markedly confused, stuporous but arousable or Comatose/unresponsive
Ascites	Absent	Slight	Moderate
Bilirubin (mg/dL)	<2	2-3	>3
Albumin (g/dL)	>3.5	2.8-3.5	<2.8
Prothrombin time prolongation (INR)	<1.7	1.7-2.3	>2.3

Child Pugh Interpretation

5-6 points	Child class A
7-9 points	Child class B
10-15 points	Child class C
